5.2.2.2 Primary Safety Endpoint

The primary safety endpoint is derived by computing the mean of Draize Scale assessed daily during each phase. The daily mean of erythema (redness) score, edema (swelling) score, bleeding score, and total score will be calculated. Total score is the sum of erythema score, edema score, and bleeding score. Descriptive statistics of the primary safety endpoint, including mean, standard deviation, median, and range will be provided by treatment, and phase. Paired difference in mean daily Draize Scale between treatment will be provided. A scatter plot for Draize Scale (y axis) vs. Day # (x axis), with different colors representing PureWick and Hollister and different panels representing study subject will also be provided.

- 5.2.3 Secondary Endpoint
 - 5.2.3.1 Questionnaire Nocturia Quality of Life (N-QoL)

The questionnaire consists of 13 items. However, the global QoL item (question 13) should be removed from the N-QoL and scored separately from the core 12 items. Question responses are scored from 0 to 4 (0 = lowest QoL, 4 = highest QoL). There are two sub-domains: sleep/energy (questions 1-5 and 7) and bother/concern (questions 6 and 8-12). Each sub-domain is made up of 6 items. The score for each sub-domain will be analyzable only if all six questions have responses. The total score is independent of the sub-domain scores, therefore patients will be allowed to miss up to one question and still have an analyzable total score.

The raw total score will be transformed onto a standardized scale of 0-100 using the following formula:

 $Transformed \ Total \ Score = \frac{The \ sum \ of \ the \ component \ items \ score}{Possible \ raw \ score \ range} * 100$

Domain scores are transformed using the same formula. Thus 0 is the worst QoL and 100 is the best QoL.

The questionnaire will be completed on Day 1, Day 15 and Day 29 of both study phases. We will categorize the questionnaire timepoint as baseline, week 1-2 (day 2-17) and week 3-4 (> day 17), respectively. If day 15 is missing, the latest record between day 2 and 17 will be used for week 1-2; if day 29 is missing, the latest record after day 17 will be used for week 3-4. Descriptive statistics will be provided by each questionnaire timepoint, treatment, and phase. A scatter plot for N-QoL (y axis) vs. Day # (x axis), with different colors representing PureWick and Hollister and different panels representing study subject will also be provided. Linear mixed model may be used, with treatment, phase, and day number as the fixed effect, and participant as the random effect.

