4.0 STUDY DESIGN

4.1 Overall Design

In this prospective, post-market, multi-site, open-label, crossover trial, women with urinary incontinence requiring the use of diapers (changes complets (Fr)) at night will be 1:1 randomized to a treatment sequence using two devices (PureWick[™] System and Hollister® Female Urinary Pouch External Collection Device) and followed for approximately 10 weeks through 2 treatment phases.

Approximately 30 female participants from 2 sites will be enrolled into the study. Those meeting eligibility criteria will be treated according to the treatment sequence assigned during randomization. Participants will be trained by the nurses for the applicable product at the beginning of each treatment phase and have access to the IFU to review during each treatment phase. The total expected duration of subject participation is approximately 10 weeks. Participants will use the device assigned in treatment phase 1 overnight while sleeping for 4 weeks (28 days) before transitioning to the second assigned device in treatment phase 2. There will be a minimum washout period of 2 weeks (not to exceed 4 weeks) between treatment phases and a re-screening of eligibility criteria before the second phase. Participants assigned to both treatment arms will place and remove the FEC (female external catheter) or FUP (Female Urinary Pouch) after standardized teaching is completed on the first day of the treatment phase.

The primary objectives are to evaluate safety (skin injury) and efficacy (capture rate). Safety will be assessed using the Draize Scale and efficacy will be measured based on daily urine capture rate. Nurses will visit participants' homes daily to perform a skin assessment and collect urine measurements during the treatment phases. Participants will be withdrawn from the treatment phase if grade 4 is achieved in any category on the Draize skin irritation scale.

The secondary objectives are to assess quality of life, tolerability, preference, comfort and ease of use. Quality of life will be measured using self-reported changes in quality of life via the validated Nocturia Quality of Life (N-QOL) and PROMIS Sleep Disturbance assessments. Preference, comfort and ease of use will be measured using subjective evaluations of the therapy via participant surveys. Tolerability will be measured by number of days of actual use of both devices, and discontinuation rate attributed to the device's discomfort or inconvenience.

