7.2.7 Days 2-7

- 1. Prior to nurse visit, participants are expected to have placed the used night pads and mesh underwear (if applicable) in their respective labeled, pre-weighed sealed bag upon completion of sleep.
- 2. Nurse will weigh and document weight of night pads and mesh underwear (if applicable).
- 3. The nurse will weigh and document the captured urine.
 - For PureWickTM Treatment Phase the captured urine volume in the PW urine collection canister will be weighed and documented.
 - For Hollister_® FUP Treatment Phase the captured urine volume in the bedside urine bag will be emptied into a graduated cylinder, then weighed and documented.
- 4. The nurse will note any signs of skin irritation or injury and document the Draize Scale score*
- 5. If during the skin assessment a Draize score of 4 is documented on the skin irritation scale in any category, this must be recorded as an AE and will require participants to discontinue from the treatment phase; participant will immediately begin wash out period and complete N-QoL.
- 6. Nurse will pre-weigh and document weight of study supplies for next night use.
- 7. The nurse will confirm the next day visit.

* For safety assessment, see section 7.3

7.2.8 Day 8

- 1. Same procedures as days 2-7.
- 2. Participant to complete Day 8 PROMIS Sleep Disturbance assessment.

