7.2.13 Days 23-28

1. Same procedures as days 2-7.

7.2.14 Day 29

- 1. Same procedures as days 2-7 with the exception of steps 6 and 7.
- 2. Participant to complete 4-week N-QOL assessment.
- 3. Participant to complete Day 29 PROMIS Sleep Disturbance assessment.
- 4. Participant to complete comfort and ease of use questionnaires.
- 5. If this day is the last day of phase 1 treatment for the participant, they will begin washout and prepare for phase 2 treatment.
- 6. If this day is the last day of phase 2 treatment for the participant, they will complete the study. Participant is to complete the End of Study Preference Survey.

7.2.15 Day 30

The participant will be asked to report any discomfort or voiding issues occurring within the first 24 hours after treatment phase completion or discharge from the study to the PI or sponsor. Skin assessments will also be conducted 24 hours after the participant completes the treatment phase and/or the study.

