7.3 Safety Assessments

7.3.1 Draize Scale

For each daily visit (described in 7.2-7.7), skin condition will be evaluated by nurses using the Draize scale (Table 1). Skin assessments will also be conducted 24 hours after the participant completes the study, either in person or virtually.

If during the skin assessment a Draize score of 4 is documented on the skin irritation scale in any category, it must be recorded as an AE and will require participants to discontinue from the treatment phase. Any other score on the skin irritation scale in any category may be recorded as an AE based on PI discretion.

To assess a potential AE identified during the home visit, the nurse will contact the PI or designee. The site will document the AE assessment on the appropriate CRF from and follow the AE until resolution. If the PI requests a follow up visit with the participant, this can be conducted on site or virtually per investigational site policy.

However, if the AE is not resolved during the treatment phase(s) within 4 weeks from the AE start date, the participant will be discontinued from the study.

Also, if during the skin assessment a Draize score of 2 or greater is documented for the device placement site, a photograph may need to be taken of the skin in the anatomical area of device application. The photo will be sent in a pseudonymized matter to the site, only the subject ID and the date when the picture was taken will be collected. These photographs will be shared with the Principal Investigator / Sub-Investigator, the Sponsor, and the study staff only and will be used for the Principal Investigator / Sub-Investigator / Sub-In

| Score | Erythema (redness) | Edema (swelling) | Bleeding |
|------------------------------|--|---|--|
| 0 | None | None | None |
| 1 ^{a} | Very slight (barely perceptible) erythema | Very slight (barely perceptible) skin surface rise | Just a visible spot of red |
| 2^a | Well-defined erythema | Well-defined skin surface rise (edges of area well-defined by definite raising) | A drop of red blood |
| 3 ^{a} | Moderate erythema | Moderate skin surface rise | A continuing ooze of red blood |
| 4 ^{b} | Severe (beet red) or damage to skin (eschar formation) | Severe skin surface rise | Significant bleeding from the sight |

 Table 1: Draize Scale for Skin Irritation

^{*a*} = Represents irritation in any category and may require participant's removal from the study based on PI decision.

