Note: a rating of 1-3 on the skin irritation scale in any category may be recorded as an AE based on PI discretion.

 b = A rating of 4 on the skin irritation scale in any category must be recorded as AE and will require participant's removal from the treatment phase and/or study.

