Endpoint data may be missing due to reasons including lost to follow-up or withdrawal of consent. For the primary efficacy endpoint, if capture rate assessments are missing for part of a treatment phase, derivation of the primary efficacy endpoint will be based on available data. For the primary safety endpoint, the main analysis will be based on available data. Sensitivity analyses may be performed for the primary safety endpoint where missing data is imputed using methods including linear interpolation or last-observation-carry-forward.

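### The primary skin-safety endpoint is summarised numerically only through a mean of available daily Draize scores; because a 4 ends the phase, an abrupt 4 from Day 6 on averages below constant barely perceptible redness

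*SAP*

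**What the plan says.** SAP 5.2.2.2 defines the endpoint: "The primary safety endpoint is derived by computing the mean of Draize Scale assessed daily during each phase". It is computed for erythema, edema, bleeding and their sum. Mean, SD, median and range are then given by treatment and phase, with the paired difference between treatments. The section also plans a plot of Draize score against day, with one panel per participant.

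On missing days, SAP 5.2.1.1 says: "For the primary safety endpoint, the main analysis will be based on available data". It adds: "Sensitivity analyses may be performed for the primary safety endpoint where missing data is imputed using methods including linear interpolation or last-observation-carry-forward".

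On a score of 4, Protocol 4.1 says: "Participants will be withdrawn from the treatment phase if grade 4 is achieved in any category on the Draize skin irritation scale". Protocol 7.2.7 requires such a score to be recorded as an adverse event and says that it "will require participants to discontinue from the treatment phase; participant will immediately begin wash out period and complete N-QoL". Protocol 7.3.1 repeats the adverse-event and phase-stop rule. Protocol 7.2.15 adds one later observation: "Skin assessments will also be conducted 24 hours after the participant completes the treatment phase and/or the study". The SAP text does not say whether that check enters the phase mean.

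**The concern.** The worst outcome stops its own scoring. A participant who scores 1 throughout contributes 28 ones. A participant who is clean and then reaches 4 contributes a run of zeros and a single 4, with nothing after it. The later the severe score occurs, the smaller the mean.

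The planned SD, median and range do not help, because they describe the participants' phase means and not their daily scores. Even the range can stay far below 4. Protocol 4.1 frames the safety objective as skin injury, and the pilot is meant to support reimbursement and a later randomised trial. A primary summary that can place a 4 below a barely perceptible 1 would mislead a reader who takes the headline comparison at face value.

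**Working it through.** The plan states no figure for this point, so there is none to reproduce. The check is direct arithmetic.

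**Inputs**
- On-device daily scores on Days 2-29, 28 in all (schedule of activities).
- Day 1 score must be 0 to start a phase (Protocol 7.2.6).
- Categories scored 0-4; 1 is barely perceptible, 4 is severe (Protocol 7.3.1, Table 1).
- No phase scores after a 4 (Protocol 4.1, 7.2.7); available data only (SAP 5.2.1.1).

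**One participant, one category, abrupt 4 on Day k, zeros before**

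Mean = 4/(k-1). Comparator: a constant 1, mean 28/28 = 1.00.

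| Day of the 4 | Mean | Against 1.00 |
|---|---|---|
| 2 | 4/1 = 4.00 | higher |
| 4 | 4/3 = 1.33 | higher |
| 5 | 4/4 = 1.00 | tie |
| 6 | 4/5 = 0.80 | lower |
| 15 | 4/14 = 0.29 | lower |
| 29 | 4/28 = 0.14 | lower |

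If Day 1 were counted, the comparison would be 4/k against 28/29 = 0.966, and the reversal would start at Day 5 (0.80). Day 6 is the cautious figure.

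**Conditions that delay the reversal**
- 24-hour check counted and still 4: 8/k is below 1 from Day 9.
- Gradual rise 1-2-3-4 ending on Day k: 10/(k-1) is below 1 from Day 12.
- Gradual rise plus a counted 24-hour 4: 14/k is below 1 from Day 15.
- Total score, 4 in all three categories, against a constant total of 1: 12/(k-1) is below 1 from Day 14.

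**Group illustration (assumed figures, not from the documents)**

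On device X, 20% of participants have an abrupt 4 on Day 15 and all other scores are 0. On device Y, everyone scores 1 on n of 28 days. Everyone contributes to both phases.
- X mean: 0.2 × 4/14 = 0.057. Y mean: n/28.
- n = 1 gives 0.036 and n = 2 gives 0.071, so X is lower from n = 2.
- For a gradual rise, X is 0.2 × 10/14 = 0.143 = 4/28: a tie at n = 4, and X is lower from n = 5.
- At n = 7 with an abrupt 4: X has mean 0.06, median 0 and range 0-0.29; Y is 0.25 throughout. The mean paired difference X-Y is 0.057 - 0.25 = -0.19. Nothing in these summaries shows that a fifth of participants on X reached 4.
- Varying the share over 10-30% and the day over 8, 15 and 22, the smallest n at which X is lower runs from 1 to 5 (abrupt) and from 2 to 13 (gradual).

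**Carry-forward to Day 29**
- One participant, abrupt 4: 4 × (30-k)/28. Day 6 gives 96/28 = 3.43, Day 15 gives 2.14, Day 22 gives 1.14, Day 23 gives 1.00 (tie) and Day 24 gives 0.86.
- Group example: 0.2 × 60/28 = 12/28 = 0.43. It restores the order up to n = 11, ties at n = 12 and fails from n = 13.

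**The case against.** The strongest reply is that no 4 is lost. Each must be recorded as an adverse event (Protocol 7.2.7, 7.3.1), and SAP 7.0 presents adverse events by device phase. The per-subject plot in SAP 5.2.2.2 would show a 4 followed by an abrupt stop, and SAP 5.2.4.2 plots each participant's maximum score per device against N-QoL. This stands, and it limits the point to the numerical primary summary. It does not remove the point: a plot, an event listing and an exploratory x axis do not give a count of worst scores by device beside the mean.

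The second reply is that this is a descriptive pilot of about 30 women with no formal hypothesis test (SAP 5.2.1.3). That also stands. A reader might infer that a wrong test decision could follow; the plan contains no test of the Draize endpoint and no ranking rule, so it could not.

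A reader might also infer that the mean could favour the device that caused severe skin injury. The documents do not support that wording. A 4 can be severe redness or swelling without skin damage, and relatedness is assessed separately (Protocol 9.3).

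The third reply is that carry-forward is available. It is optional, it assumes that the 4 persists after the device is removed, and it fails late in the phase. The other method named, linear interpolation, needs a later score and cannot by itself fill days after a terminal stop.

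Finally, the table shells (SAP Appendix 1) and derived data specification (Appendix 2) are not available here. They may hold a worst-score table or settle how Day 1 and Day 30 are treated. The arithmetic is certain; the omission is certain only for the SAP text.

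**Conclusion.** The point stands for the numerical summary of the primary safety endpoint and should be fixed. With one category, zeros before the 4 and the 24-hour check not counted, an abrupt 4 averages below a constant 1 from Day 6. Under the other trajectories examined the reversal starts between Day 9 and Day 15. The result depends on timing: an abrupt 4 on Days 2-4 still averages above 1, so it would be wrong to say that the mean hides every severe score. The group figures are illustrations with an assumed share, day and comparator.

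The consequence is a primary mean and paired difference that can look better for a device on which participants reached a 4. It is not that severe scores go unreported, nor that the mean is the only display of skin data in the plan.

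One related gap remains. Phase stops for skin irritation have no stated table: SAP 5.2.3.4 covers discomfort or inconvenience, and SAP 6.1 gives reasons for leaving the study, although it draws on the phase completion forms.

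**What to change.** In SAP 5.2.2.2 keep the mean and add, by device and with the within-participant comparison:

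1. Each participant's worst on-device Draize score per phase, for each category, as number and percent at 0, 1, 2, 3 and 4.
2. The number and percent with any 4 and, as a separate row, the number whose phase was stopped for skin irritation at a lower score.

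Report counts, not only an average of worst scores. In the 20% example the average worst score is 0.2 × 4 = 0.8 on X and 1.0 on Y, which still makes X look better.

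If the Appendix 1 shells already contain this table, naming it in 5.2.2.2 is enough. Carry-forward may stay optional; if it is run, state its limit (against a constant 1, a tie at Day 23 and failure from Day 24).

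The cost is a short SAP edit and a few table rows. The daily scores and phase completion status are already collected, and no clinical rule changes.

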5.2 Exclusion Criteria

Participants are excluded from the study if any of the following criteria apply:

- 1. Has frequent episodes of bowel incontinence without a fecal management system in place; or
- 2. Has moderate to heavy menstruation and cannot use a tampon or menstrual cup; or
- 3. Has Urinary tract, vaginal or other chronic infections, active genital herpes; or
- 4. Has Urinary retention; or
- 5. Is agitated, combative, and/or uncooperative and may remove the external catheter or pouch; or
- 6. Has any wound, open lesion or irritation on the genitalia, perineum, or sacrum; or
- 7. Has any pre-existing neurological, psychiatric, or other condition that would confound quality of life assessment or would make it difficult to self-report on quality-of-life questionnaires in the opinion of the investigator; or
- 8. Is known to be pregnant at time of enrollment (for women of childbearing age); or
- 9. Any other condition that, in the opinion of the investigator, would preclude them from participating in the study.
- 10. Is under supervision of a legally authorized representative.

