7.2.16 Days 29-42 (+14) Wash Out Period

Participant begins washout period of 2 weeks (not to exceed 4 weeks) between treatment phase 1 and treatment phase 2. At the completion of washout, the nurse will perform a rescreening of eligibility criteria before phase 2 treatment begins.

7.2.17 Treatment Phase 2

Same procedures as outline in sections 7.2 - 7.11.

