7.6 Replacement of Participants

A participant that discontinues from the study will be replaced when feasible.

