8.0 PARTICIPANT DISCONTINUATION/WITHDRAWAL

8.1 Discontinuation/Withdrawal

- A participant may withdraw from the study at any time at his/her own request or may be withdrawn at any time at the discretion of the investigator or sponsor for safety, behavioral, compliance, or administrative reasons. This is expected to be uncommon.
- At the time of discontinuing from the study, no further assessments will be performed.
- If the participant withdraws consent for disclosure of future information, the sponsor may retain and continue to use any data collected before such a withdrawal of consent.
- Participants who withdraw or discontinue the study early may be replaced.

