5.2.2 Primary Endpoint

5.2.2.1 Primary Efficacy Endpoint

Capture rates is evaluated daily during participant phase 1 and phase 2. Daily capture rate (%) is defined as:

captured urine weight / (captured urine weight + leaked urine weight) *100

The primary efficacy endpoint is derived by computing the mean of daily capture rate during each phase. Descriptive statistics of the primary efficacy endpoint, including mean, standard deviation, median, and range will be provided by treatment and phase. A scatter plot for Capture Rate (y axis) vs. Day # (x axis), with different colors representing PureWick and Hollister and different panels representing study subject will also be provided. The summary statistics (mean, 95% CI for mean, median) for paired difference in mean daily capture rate between the two treatment arms and p-value from Wilcoxon signed rank test or Paired t-test will be provided. Normality test will be performed before the test, if the data is normally distributed then Paired t-test will be used, otherwise Wilcoxon signed rank test will be used. Sensitivity analyses using linear mixed model (with treatment, phase, and study day as the fixed effect, and participant as the random effect), beta regression (with treatment, phase, and study day as the fixed effect, and participant as the random effect) will also be performed.

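### The only planned between-device Draize contrast drops women kept out of Phase 2 by Phase 1 skin irritation, and no all-available-data contrast with an interval is planned

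*SAP*

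**What the plan says.** SAP 5.2.2.2 derives the mean daily Draize score per phase (erythema, edema, bleeding and total). It plans summaries, "Descriptive statistics of the primary safety endpoint, including mean, standard deviation, median, and range will be provided by treatment, and phase", per-subject plots, and one between-device contrast: "Paired difference in mean daily Draize Scale between treatment will be provided". It names no interval, test or model for Draize.

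Capture rate is treated differently. SAP 5.2.2.1 gives its paired difference a 95% CI and adds "Sensitivity analyses using linear mixed model (with treatment, phase, and study day as the fixed effect, and participant as the random effect"), together with a beta regression.

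For missing Draize data, SAP 5.2.1.1 uses available data. It allows optional sensitivity analyses in which "missing data is imputed using methods including linear interpolation or last-observation-carry-forward".

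The protocol links Phase 2 entry to skin condition by several routes:

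- After washout, "the nurse will perform a rescreening of eligibility criteria before phase 2 treatment begins" (Protocol 7.2.16). One exclusion is "Has any wound, open lesion or irritation on the genitalia, perineum, or sacrum" (Protocol 5.2, item 6).
- Protocol 7.2.6 requires a Draize score of 0 before treatment starts and allows up to 4 weeks from the original baseline visit to reach it. Protocol 7.2.17 carries the same procedures into Phase 2, and the schedule shows Draize scoring at the Phase 2 baseline.
- Protocol 7.3.1 discontinues a woman from the study if an AE has not resolved within 4 weeks of its start. The notes to its Table 1 allow removal from the study for scores 1 to 3 at the investigator's decision, and require removal from the phase and/or the study for a score of 4.

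After that, "At the time of discontinuing from the study, no further assessments will be performed" (Protocol 8.1), and "A participant that discontinues from the study will be replaced when feasible" (Protocol 7.6).

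**The concern.** Comparing skin safety is a primary objective. A woman who never starts Phase 2 has no on-device score for her second device and forms no pair. If Phase 1 irritation is the reason, her high score is removed from the contrast, so the loss depends on the outcome itself. If the more irritating device bars more women, the paired figure most likely moves toward no difference. Replacement can restore the number of pairs but not the women who were lost.

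Nothing else planned clearly fills the gap. Interpolation and last observation carried forward cannot supply scores on a device never worn. The poolability regression in SAP 5.2.1.2 has a treatment term, but it is aimed at site, has no participant or phase term and states no interval. SAP 5.2.1.3 makes confidence intervals optional.

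At stake is an estimate meant to support reimbursement and help plan the later randomized trial. An attenuated skin difference, with no interval and no stated number of pairs, could mislead on both.

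**Working it through.** The plan states no Draize effect, SD, irritation rate or dropout rate, so there is no figure of its own to reproduce. The check is illustrative.

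**Inputs.** From the documents: about 30 women, 1:1, hence 15 per sequence. Assumed, with no anchor in the documents: phase-mean Draize total 2.0 if irritated and 0.2 if not; 20% irritated by device A and 5% by device B; a fraction *b* of women irritated in Phase 1 barred from Phase 2, with *b* = 0.10, 0.25 or 0.50.

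**True difference.** (2.0 − 0.2) × (0.20 − 0.05) = 1.8 × 0.15 = 0.27.

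**Women barred.** 15 × 0.20*b* after A plus 15 × 0.05*b* after B = 3.75*b*, that is 0.4, 0.9 or 1.9 of 30.

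**Paired expectation.** Let *p* be the probability that both devices irritate the same woman. Per 15 women, among those not barred:

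- A first: irritated by A 0.20(1 − *b*), by B 0.05 − *bp*; pairs 1 − 0.20*b*
- B first: irritated by A 0.20 − *bp*, by B 0.05(1 − *b*); pairs 1 − 0.05*b*

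Summing A minus B, the *bp* terms cancel and leave 0.15(2 − *b*) over 2 − 0.25*b* pairs. So

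paired = 0.27 × (2 − *b*) / (2 − 0.25*b*), whatever the within-woman correlation.

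- *b* = 0.10: 0.27 × 1.90 / 1.975 = 0.260
- *b* = 0.25: 0.27 × 1.75 / 1.9375 = 0.244
- *b* = 0.50: 0.27 × 1.50 / 1.875 = 0.216

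**Simulation of the alternatives** (latent correlation 0, 0.5, 0.8; truth 0.27):

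| *b* | Paired | Difference of by-treatment means | Mixed model |
|---|---|---|---|
| 0.10 | 0.259–0.261 | 0.269–0.271 | 0.265–0.269 |
| 0.25 | 0.243–0.244 | 0.269–0.271 | 0.262–0.270 |
| 0.50 | 0.216–0.217 | 0.269–0.271 | 0.251–0.271 |

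Replacing barred women until there are 30 pairs leaves the paired figure at 0.259–0.261, 0.244–0.245 and 0.215–0.216.

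**Size against sampling error.** In trials of 30 women the paired SE is 0.115–0.148. The largest shift relative to its SE is 0.055 / 0.115 = 0.48. Total error (RMSE) is 0.121–0.149 paired, 0.124–0.151 for by-treatment means, 0.127–0.152 for the mixed model and 0.211–0.213 for Phase 1 alone.

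**Other cases.**

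- Equal devices (10% irritated each, *b* = 0.50): every estimator averages 0.00.
- Equal numbers barred (A 25% of 20%, B all of 5%): paired 0.252–0.277, mixed 0.247–0.271.
- Only B bars (all of its 5%): paired 0.282–0.314, by-treatment 0.238–0.270, mixed 0.248–0.270. The direction reverses.

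**A second data model.** Assume continuous scores with SD 0.5, means 1.1 and 0.6 (truth 0.50), within-woman correlation 0.3 to 0.7, and Phase 2 not started when the Phase 1 mean reaches 1.75, 1.5 or 1.25. Losses are then 9%–39% after the worse device and 1%–10% after the better one. The paired figure averages 0.44–0.49, the difference of by-treatment means 0.50–0.55, and a maximum-likelihood estimate on all available data 0.49–0.51. Here subtracting the by-treatment means can overstate the difference.

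**The case against.** The strongest reply is that the remedy gains nothing in total error. By the figures above, the mixed model's RMSE at 30 women is no lower than that of the paired difference. When only the less irritating device bars women and correlation is strong, the model is no closer to the truth (0.248 against 0.282; truth 0.27). The shift is hundredths of a point on a total that runs from 0 to 12, in a pilot with no test and no acceptance criterion. Every rate is assumed. The protocol also favours return: a Draize 4 sends a woman to washout (7.2.7), washout lasts 2 to 4 weeks, and a failed skin check can be rescheduled.

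Much of the information is planned anyway. The Draize summaries by treatment and phase keep these women. SAP 7.0 attributes AEs to devices, with washout AEs assigned to the Phase 1 device, and SAP 6.1 reports discontinuation by reason. The table shells in SAP Appendix 1 are not visible and might already contain the split or the pair count. The missing interval is partly a general choice to stay descriptive.

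These points stand and limit the weight of the finding. They do not remove it. Irritation that resolves bars nobody, but the routes for irritation that persists are written into the protocol. Subtracting the planned summaries carries no interval and is not reliable under the second data model. AE tables count events and do not estimate the Draize difference. The case rests on bias and transparency, not on precision.

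**Conclusion.** The concern holds. The paired difference is the only between-device Draize contrast in SAP 5.2.2.2. Women kept out of Phase 2 by skin irritation cannot enter it, and no Draize contrast on all available data with an interval is planned.

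Under the assumed rates the paired figure is 0.22 to 0.26 against a truth of 0.27, and 0.44 to 0.49 against 0.50 in the second model. The pull is toward no difference when the more irritating device bars more women, absent when the devices are equal, and reversed when only the less irritating device bars women. In the first model, where it was compared with sampling error, the shift stays below half a standard error. Real size and direction cannot be known from the documents. This is a modest bias on a primary endpoint, worth correcting because correction costs little.

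**What to change.** In SAP 5.2.2.2 add, at least for the Draize total, a linear mixed model of the phase mean with treatment and phase fixed and participant random, fitted to all available phases, with a 95% CI. It resembles the model already planned for capture rate.

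Beside the paired difference, state the number of pairs out of the women who started Phase 1. In the SAP 6.1 disposition table, show women not starting Phase 2 for skin reasons by Phase 1 device. A Phase 1-only difference may be added as a supportive check, but it is clearly less precise.

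The cost is SAP wording, one model, one count and one table split, all from data already collected, with no change to conduct. The model's interval will differ slightly from a paired one and is approximate with 30 women and skewed scores. The model can also leave a small residual bias, up to about 0.02 below the truth of 0.27 in the cases run.
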